Evaluation criteria	
Primary criterion:
 
Patient satisfaction and experience are assessed by 2 questionnaires, on D30 and D90: the CSQ-8 questionnaire and the "You and your management by your home healthcare provider" questionnaire.
 
With the CSQ-8, the patients' overall satisfaction with their management in general is determined by a score above 20 points (on a scale from 8 to 32) on D30. Maintenance of satisfaction is measured on D90 by a score above 20 points which has not decreased by more than 4 points compared with D30.
 
The safety profile with the questionnaire "You and your management by your home healthcare provider". The answers to all questions with 5 possible choices and the scores based on the scales from 1 to 10 will be described.
 
Secondary criteria:
 
Home healthcare provider (PSAD) management:
 
 ○ PSAD management is described during the different phases (pre-installation, installation, follow-up), by the number of interactions, their type (visits / telephone calls), the time spent, the reason for these interactions and, for the visits, by their location (home / hospital).

- The management observed is also described for all the "closed-loop" systems used in the study according to whether or not these interactions were set out in the opinion of the HAS (French National Authority for Health) dated 28 January 2020 for the [REDACTED] system, and is therefore compared with the management initially scheduled for conducting the study (number of visits or telephone calls made versus those scheduled).
- The knowledge acquired by the patient during their initial training is evaluated by the PSAD nurse using the acquired knowledge assessment questionnaire on D1/D3, D30 and D90.
- The satisfaction of the PSAD nurses is assessed with the **PSAD satisfaction questionnaire**. This questionnaire is completed once by each PSAD nurse at the end of the study (after the D90 of the last patient at the centre). It takes into account the PSAD nurse's opinion on all of the services they provide.

Patient questionnaires:

- The patient's profile in terms of their experience with medical devices is assessed by the "**You and medical devices**" questionnaire completed at the time of inclusion.
- The patient's feelings about their current and future state of health are assessed by the "**You and your health**" questionnaire completed at inclusion and on D90.

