Statistical methodology	
The reference population for the statistical analysis will be all of the included patients, fitted with the device who meet all of the inclusion and exclusion criteria.
 
Analysis of the primary criterion:
 
The overall CSQ-8 score will be calculated at each time of assessment. The percentage of patients satisfied on D30 and D90 and the percentage of patients with continued satisfaction on D90 will be described. The 95% confidence intervals (CIs) will also be presented.
 
The absolute variation of the overall CSQ-8 score and the relative variation in relation to D30 will also be described on D90.
 
The answers to all the items in the "You and your management by your home healthcare provider" questionnaire will be described using percentages for the questions with 5 possible choices. Scores based on the scales from 1 to 10 will be presented using descriptive statistics.
 
Analysis of the secondary criteria:
 
A descriptive statistical analysis of all the secondary parameters will be carried out as a whole and according to the study phase when applicable (pre-installation, installation and follow-up).
 
All questionnaire items will be described using descriptive statistics and scores where applicable.
 
The evolution of HbA1C will be described at the end of the study. Blood sugar parameters will be described at inclusion, on D30 and D90.
 
To describe patient safety, the incidence rate of all adverse events and serious adverse events (SAEs), and those related to the "closed-loop" automated insulin delivery system (or "artificial pancreas"), will be presented as a whole and by "System Organ Class" and "Preferred term" in the MedDRA terminology. The number of episodes of severe hypoglycaemia requiring the intervention of a third party for glucose administration and the number of episodes of hyperglycaemia with ketosis will also be described.
 
In addition, the number of incidents associated with the device will be described.

TABLE OF CONTENTS

COORDINATING INVESTIGATOR:	5
SPONSOR:	5
DATA PROTECTION OFFICER:	5
RESEARCH AND DEVELOPMENT CENTRE:	5
• MEDICAL VICE PRESIDENT	5
• DIRECTOR OF REAL WORLD & CLINICAL EVIDENCE	5
• STUDY PHYSICIAN	5
• HEAD OF BIOMETRICS	5
• PROJECT MANAGER	5
• BIOSTATISTICIAN	5
I - INTRODUCTION	24
I.1 - Background.....	24
I.2 - Medical Devices.....	25
I.3 - Study rationale	26
II - OBJECTIVES OF THE STUDY	26
II.1 - Primary objective.....	26

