- Hearing the audible alarms of my treatment equipment (pump, glucose sensor, etc.)

There is no specific score, the answers are evaluated independently of one another.

You and your management in general (CSQ-8: Overall satisfaction)

The patient's overall satisfaction with their management is assessed by the CSQ-8 (Client Satisfaction Questionnaire) (28) (29). This is a validated French-language questionnaire, which consists of 8 questions. It measures the patient's direct satisfaction with specific services provided and received within a given time frame and specific service framework. It is used to describe the effect of PSAD management on this overall patient satisfaction during the follow-up. Each question is answered using a 4-point scale (e.g. 1. poor, 2. average, 3. good, 4. excellent).

The score ranges from 8 to 32, with higher values indicating higher satisfaction^{22, 23}.

You and your management by your home healthcare provider (Proactiveness / availability / PSAD advice)

The patient's targeted experience / satisfaction is assessed by an ad-hoc questionnaire entitled: "You and your management by your home healthcare provider" developed by the French Diabetes Federation (FFD).

The questionnaire assesses the proactiveness, availability and PSAD nurse advice. It is used to measure patients' overall satisfaction with their management by the PSAD during the follow-up.

It is composed of:

- 13 questions answered using a 5-point scale
- 3 scales from 1 (no confidence at all) to 10 (complete confidence).

There is no specific score, the answers are evaluated independently of each other.

VI.10.6 - PATIENT ACQUIRED KNOWLEDGE ASSESSMENT

QUESTIONNAIRE

The knowledge acquired by the patient is assessed via an ad-hoc questionnaire, developed by the sponsor. The questionnaire is completed by the PSAD nurse and each item is recorded in the e-CRF.

The questionnaire is divided into 2 parts:

- Learning the basic functions
- Learning the advanced open-loop functions/settings.

Part one contains 12 sections, each evaluating between 4 and 12 items. The 12 sections relate to knowledge on:

- Precautions for use of the components
- Data visualization software
- Initialisation of the control module/terminal
- Reading the control module/terminal screen
- Control module/terminal menu
- Remote-control mode
- Use of the pump
- Cartridge
- Catheter
- Sensor
- Alarms/Alerts/Information
- Various knowledge (on-call support, procedure to follow, etc.).

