Check procedures for the reliability and validity of the data collected with the e-CRF will be defined and described in a data validation plan. These procedures will be defined to ensure the validity of the data in relation to the study's objectives and context. These checks will focus on the completeness and plausibility of the recorded values (bounds checking) and the compatibility of the various data (consistency checking). These checks will generate requests for clarification at the end of data entry on each page of the e-CRF.

After performing data entry and resolving any requests for correction in the e-CRF, the investigator and PSAD nurse will validate all of the recorded data. They will each sign once per patient the data recorded in the e-CRF for which they are responsible, using their login details and access code.

After entering the data for all patients in the e-CRF, a data review meeting will be organised using tables, listings and graphs representing the database content. The strategy for factoring in missing, inconsistent or other problematic data will be determined in collaboration with the sponsor. All deviations from the Protocol will also be described, in particular the list of erroneously included patients. If it becomes necessary to define different patient populations for analysis, these populations will also be described. All decisions made during the data review, prior to analysis, will be recorded in a specific report kept in the Trial Master File.

Once this report has been approved, the patient database will be locked and sent to the statistician for analysis.

X - STATISTICAL ANALYSIS

X.1 - THE SAMPLE SIZE

For reasons of feasibility, the number of patients to be included in the study was set at 35, for a number of expected evaluable subjects fixed at 32. Should any patients leave the study between the time of inclusion and the beginning of fitting the "closed-loop" automated insulin delivery system (or "artificial pancreas"), they will be replaced.

This number of patients will be sufficient to estimate the percentage of patients satisfied on D90 with their management by the PSAD (the primary objective of the study), with an accuracy of $\leq 12.4\%$.

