In fact, whatever the criterion considered (satisfaction estimated from the CSQ-8 and satisfaction assessed from the answers to the various questions in the questionnaire "You and your management by your home healthcare provider" on D90), the expected percentage of satisfied patients is $\geq 85\%$. The formula used to estimate the accuracy is obtained from the definition of the 95% bilateral confidence interval (CI 95%) for a proportion p , with normal approximation

$$E = \sqrt{(1.96^2 p (1-p)) / n}$$

With $n=32$ evaluable patients, the accuracy will therefore be $\leq 12.4\%$.

X.2 - ANALYSIS POPULATIONS

X.2.1 - DEFINITION OF THE POPULATIONS

The following analysis populations will be defined:

- **Included patients:** all patients included in the study who have signed a consent form
- **Intent-to-treat patients:** all of the included patients fitted with the device who meet all of the inclusion and exclusion criteria
- **PSAD nurses:** all PSAD nurses who answered the PSAD satisfaction questionnaire
- **Investigators:** all investigators in the study

X.2.2 - DEVIATION FROM THE PROTOCOL

Before the database is frozen, deviations from the Protocol related to the inclusion/exclusion criteria will be reviewed.

Patients who do not meet all of the inclusion/exclusion criteria will not be included in the intent-to-treat patient population.

X.3 - STATISTICAL ANALYSES

A Statistical Analysis Plan (SAP) will be drafted by the CRO in charge of the study and validated by the sponsor before the database is frozen. Statistical analyses will be carried out in SAS® version 9.2 or higher (SAS institute, North Carolina, USA).

X.3.1 - GENERAL CONSIDERATIONS

The continuous variables will be described in terms of mean, standard deviation, median, 1st and 3rd quartiles and extreme values. The categorical variables will be described in terms of absolute frequency and percentage per category. Ordinal variables will be described using the most appropriate method (continuous variables or categorical variables). Open-ended responses to questionnaires developed on an ad-hoc basis will be presented in the form of a list.

95% bilateral confidence intervals (CI 95%) of percentages and/or averages will be calculated when deemed relevant. The confidence intervals of the percentages will be calculated using the Agresti-Coull method. For averages, the Wald 95% CIs will be calculated.

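### The stated accuracy of at most 12.4% is a Wald figure; the planned Agresti-Coull interval gives 12.8% at 85% and n = 32, and no satisfied percentage is defined for the PSAD questionnaire it also covers (minor)

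*Combined protocol and SAP*

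**What the plan says.** Section X.1, repeated in the synopsis, sets the size on practical grounds: "For reasons of feasibility, the number of patients to be included in the study was set at 35", with 32 expected to be evaluable. It then adds a precision statement: "This number of patients will be sufficient to estimate the percentage of patients satisfied on D90 with their management by the PSAD", to within 12.4% at most. The expected proportion is put at 85% or more, and the claim is said to hold "whatever the criterion considered (satisfaction estimated from the CSQ-8 and satisfaction assessed from the answers to the various questions in the questionnaire" on PSAD management.

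The method behind the figure is declared: "The formula used to estimate the accuracy is obtained from the definition of the 95% bilateral confidence interval (CI 95%) for a proportion", using the normal approximation.

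Section X.3.1 names a different method for reporting: "The confidence intervals of the percentages will be calculated using the Agresti-Coull method".

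For the CSQ-8, X.3.4 plans the percentages satisfied on D30 and on D90 and the percentage with continued satisfaction on D90, with 95% intervals. For the PSAD questionnaire (13 five-point questions and three scales from 1 to 10), VI.10.5 says: "There is no specific score, the answers are evaluated independently of each other". The synopsis plans description only: "The answers to all questions with 5 possible choices and the scores based on the scales from 1 to 10 will be described", "using percentages for the questions with 5 possible choices". VII.1 and X.3.4 likewise stay at item level.

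**The concern.** A precision statement should describe the interval that the report will print, for a result that the plan defines. There are two mismatches.

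- **Method.** X.1 quotes the half-width of one interval and X.3.1 plans another. At the planning inputs the planned interval is slightly wider. It is also not centred on the estimate, so one plus-or-minus figure hides how far the lower limit falls.
- **Scope.** X.1 extends both the 85% and the 12.4% to the PSAD questionnaire. No section says which answers, on one item or across items, make a patient satisfied. The claim for that part of the primary criterion therefore cannot be checked against a defined output.

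What is at stake is modest: how the precision is read, and whether a satisfied group for the PSAD items might be chosen after answers have been seen. X.3 requires the SAP to be validated only before the database freeze, while IX.2 places a data review with tables and listings before lock.

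**Working it through.** **Inputs.** n = 32, p = 0.85 and z = 1.96, all from X.1; the reporting method is from X.3.1.

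**1. The plan's own figure (Wald).**
E = 1.96 × sqrt(0.85 × 0.15 / 32) = 0.1237, or 12.37%. The stated 12.4% reproduces. As an interval this is 72.6 to 97.4%.

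**2. The planned interval (Agresti-Coull) at the same inputs.**
- x = 0.85 × 32 = 27.2
- adjusted n = 32 + 1.96² = 35.84
- adjusted p = (27.2 + 1.92) / 35.84 = 0.8125
- half-width = 1.96 × sqrt(0.8125 × 0.1875 / 35.84) = 0.1278, or 12.78%
- limits: 81.25 − 12.78 = 68.47% and 81.25 + 12.78 = 94.03%
- distance from 85%: 16.53 points below and 9.03 points above

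The half-width is 12.78 − 12.37 = 0.41 points larger. The lower limit is 72.63 − 68.47 = 4.16 points lower than the Wald limit.

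**3. Agresti-Coull at exactly 85%, by n.** n = 33: 12.58%; n = 34: 12.39%; n = 35: 12.20%. The 12.4% is met from n = 34.

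**4. Counts that can occur with n = 32.** The value 27.2 is not a possible count, so the neighbouring ones matter:

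| Satisfied | Observed | Wald half-width | Agresti-Coull half-width | Agresti-Coull limits | Estimate minus lower limit |
|---|---|---|---|---|---|
| 27/32 | 84.4% | 12.58 | 12.92 | 67.8 to 93.6% | 16.6 |
| 28/32 | 87.5% | 11.46 | 12.16 | 71.3 to 95.6% | 16.2 |
| 29/32 | 90.6% | 10.10 | 11.27 | 75.0 to 97.5% | 15.6 |
| 30/32 | 93.8% | 8.39 | 10.22 | 78.8 to 99.3% | 14.9 |

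At n = 32 the 12.4% is exceeded at 27/32 and met at 28/32 under either method. The lower limit, however, lies more than 12.4 points below the estimate in every row.

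**5. Scope, set side by side.**

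| | CSQ-8 | PSAD questionnaire |
|---|---|---|
| Score | Total from 8 to 32 (VI.10.5) | None (VI.10.5) |
| Rule for satisfied | Above 20 (VII.1) | None |
| Planned result | Percentages satisfied and with continued satisfaction (X.3.4) | Category percentages and scale summaries, item by item (VII.1, X.3.4, synopsis) |
| 95% interval committed to | Yes (X.3.4) | No; X.3.1 allows one where judged relevant |
| Covered by the 85% and 12.4% | Yes (X.1) | Yes (X.1) |

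**The case against.** The strongest reply is that X.1 contains no mistake. It names the normal approximation, and the number follows from it. Planning with a simple formula and reporting with a better-behaved interval is ordinary practice. The claim is also conditional on 85% or more, and every count of 28/32 or higher has an Agresti-Coull half-width of at most 12.2%. Recruitment ends at 35 fitted patients (section III), so 34 or 35 may be analysed, and then the 12.4% holds even at exactly 85%. All of this stands, and it is why the point is minor. It does not make the printed figure the half-width of the planned interval at the planning inputs, nor does it show the longer lower side.

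Four stronger readings are tempting, and the documents do not support them:

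- **That 12.4% is an arithmetic error, or that the bound fails outright.** It reproduces, and it holds at every attainable result of 85% or more.
- **That the study is too small or needs 34 evaluable patients.** The number was set for feasibility, and no test or success threshold depends on it.
- **That X.1 leaves open which D90 CSQ-8 percentage it means.** X.1 speaks of patients satisfied on D90, and X.3.4 lists that separately from continued satisfaction. The natural reading is a score above 20.
- **That the 12.4% is contradicted by the precision of single answer categories on the PSAD items.** X.1 claims nothing for percentages below 85%.

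On the PSAD questionnaire, the defence can fairly say that category percentages are planned, that a satisfied percentage could be built from them once the categories are named, and that the SAP still to be drafted could name them. That is correct, but the current text neither names them nor requires them to be named before the answers are reviewed.

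**Conclusion.** The point holds as a minor one. At 85% and n = 32 the planned interval has a half-width of 12.8%, not 12.4%, and runs from 68.5 to 94.0%. The gap is 0.4 points in half-width, and no sample size or decision changes. For the PSAD questionnaire, the 85% and 12.4% match no defined result.

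This rests on two assumptions: that Agresti-Coull in X.3.1 applies to the D90 CSQ-8 percentage, as its general wording indicates, and that 32 patients contribute a D90 answer. With 34 or 35, the 12.4% would be met at 85%. The response labels of the PSAD items are not in the documents, so nothing is claimed about which answers ought to count as satisfied.

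**What to change.** In X.1 and the synopsis:

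1. Restate the precision with the planned interval: Agresti-Coull, about 12.8%, that is 68.5 to 94.0% at 85% and n = 32. Giving the limits shows the asymmetry that a single figure hides.
2. Limit the statement to the CSQ-8 percentage satisfied on D90, written out as a score above 20.
3. If the PSAD questionnaire is to remain covered, state before any data review which answers count as satisfied, and add those percentages with 95% intervals to X.3.4.

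Items 1 and 2 are wording only and need no extra patients. The third adds a definition and a few intervals. The price is a stated precision that is slightly less favourable and narrower in scope.

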Patients have the right to withdraw from the study at any time and for any reason, without prejudice to their future medical monitoring. They will then have the device removed. All data collected up to the time they leave the study will be kept for analysis, but no other data concerning them will subsequently be collected.

For each patient, it will be specified whether they terminated the study early for any of the following reasons:

- Adverse event.
- Withdrawal of consent.
- Patient lost to follow-up.
- Non-compliance with at least one inclusion/exclusion criterion.
- Investigator's decision:
 - o Patient considered unfit by the investigator
 - o Other, to be specified
- Other, to be specified.

In the event of early termination of the study for a patient, the information (date and reason for leaving) will be reported by the investigator in the patient's medical file and entered in the e-CRF. In the event of early termination of the study due to an adverse event, the adverse event will be followed up until it is resolved or stabilised.

V - MEDICAL DEVICES

V.1 - PRESENTATION OF THE "CLOSED-LOOP" AUTOMATED INSULIN DELIVERY SYSTEM (OR "ARTIFICIAL PANCREAS")

In this study, patients will be fitted with a "closed-loop" automated insulin delivery system (or "artificial pancreas").

This system combines 3 medical devices:

- An insulin pump,
- A continuous glucose sensor (CGM),
- And an algorithm that continuously calculates the amount of insulin needed for glycaemic control and controls the insulin pump.

To help keep the patient's glucose levels as close to the desired value (e.g. 120 mg/dl) as possible, and within the target (e.g. between 70 and 180 mg/dl), the CGM measures the glucose concentration approximately every 5 minutes. The measured glucose value is transmitted from the sensor to the algorithm via Bluetooth. The algorithm compares this value with the set target value and calculates:

- Either the insulin requirement based on the difference between the glucose value and the target value. According to the result, the pump's base flow rate adapts to each measurement (increase or decrease).
In this case, the insulin pump receives the command to deliver the specific quantity of insulin and the subcutaneous injection begins.
- Or the sugar requirement, if the glucose value is lower than the target value.

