^e: Metabolic balance includes the daily average blood sugar level and its variability, the time spent in hyperglycaemia (>180 mg/dl, [180-250 mg/dl] and > 250 mg/dl), normoglycaemia [70-180 mg/dl] and hypoglycaemia (<70mg/dl, [54-70 mg/dl] and < 54 mg/dl), and % of time spent in closed loop (if available).

^f: At the prescriber's request, the sensor can be installed prior to installing the complete "closed-loop" automated insulin delivery system (or "artificial pancreas"), and this can be done either in hospital by hospital staff or at the patient's home during a pre-installation visit by the PSAD nurse.

^g: At the patient's request.

^h: Collection of adverse events only (unless the sensor is installed during the pre-installation phase).

ⁱ: Completed once, at the end of the study (after the last patient has left the centre).

Details of the patient questionnaires

	Inclusion	D30	End of the study - D90 (or early withdrawal)
You and the "closed-loop" automated insulin delivery system (or "artificial pancreas") (Expected benefits / Perceived benefits)	X	X	X
You and your quality of life with diabetes (EQ-5D-5L (24) (25) (26))	X	X	X
You and your beliefs about the medical treatment (BMQ (27) – specific section only)	X	X	X
You and medical devices (Patient profile / MD experience)	X		
You and your health (Patient profile / state of health)	X		X
You and your daily constraints	X	X	X
You and your management in general (CSQ-8 (28) (29): Overall satisfaction)		X	X
You and your management by your home healthcare provider (Proactiveness / availability / PSAD advice)		X	X
You and your quality of life and daily constraints linked to the risk of hypoglycaemia episodes (HFS-II) (30) (31)	X	X	X

VI.2 - INCLUSION VISIT (DAY -15 ± 10 DAYS)

An investigator carries out the patient's inclusion visit in the hospital centre.

Patients meeting the eligibility criteria are invited to participate in the study.

The investigator then gives the patient an information leaflet and explains the study (procedure, objectives, benefits and risks, etc.) and answers any questions they may have. If the patient agrees to participate in the study, they give their free and informed consent by dating and signing the consent form. The information will be transferred to the patient's source file, and the study procedures described below can begin (see details in section VI.10):

- Demographic data
- Socio-professional data
- History of diabetes including date of diagnosis and complications

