- A reminder of the safety rules.
- A review of anything that has not been understood.
- A check of the terminal, including its proper maintenance and the patient's correct understanding of how it works.
- A check of the pump and its proper maintenance.
- A check of the interstitial glucose measurement system and its proper maintenance.
- Verification that the patient still has their replacement scheme and whether it has been made use of, as well as the expiration dates for the insulin, pen and emergency kit.
- An evaluation of the consumption of consumables
- The collection of any adverse events / SAEs / incidents. If an adverse event is reported, the PSAD nurse passes the information on to the investigator for patient assessment and monitoring if necessary
- Collection of partially used and unused boxes by the PSAD nurse. However, used boxes are not collected.

At the end of the interview, the PSAD nurse records this visit in the PSAD files and completes the e-CRF. The PSAD nurse sends the investigator a written report with an assessment of the patient's training and a list of adverse events (where applicable).

After the last follow-up of the last patient included on D90 in the hospital centre, the PSAD nurse completes the PSAD Satisfaction Questionnaire in the e-CRF.

VI.9 - END-OF-STUDY VISIT

The end-of-study visit is carried out approximately 3 months (\pm 15 days) after the "closed loop" automated insulin delivery system (or "artificial pancreas") is installed. An end-of-study visit will be carried out for all patients. If the patient ends their participation in the study before its scheduled end, the patient's condition, date and the reason for termination will be documented in the patient's medical file and reported in the e-CRF.

For this end-of-study or early discharge visit, the patient will attend the hospital and undergo the following procedures (if possible):

- HbA1c blood test

- Metabolic balance over the last 4 weeks:
 - Daily average blood sugar level and its variability (standard deviation and coefficient of variation, if applicable)
 - Time spent (as a percentage):
 - In hyperglycaemia (> 180 mg/dl), [180-250 mg/dl] and > 250 mg/dl
 - In the blood sugar target [70-180 mg/dl]
 - In hypoglycaemia (< 70 mg/dl), [54-70 mg/dl] and < 54 mg/dl
 - % of time spent in closed loop (if available)
- D90 patient booklet including the following questionnaires:

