The number of patients is small and the proportion of expected missing or invalid data is small and randomly distributed. Consequently, no imputation procedure for missing or invalid data will be applied. If necessary, the replacement of some of these data will be detailed in the SAP on a case-by-case basis.

X.3.2 - AVAILABILITY OF THE PATIENTS

The number of patients included, fitted with the device, prematurely discharged before being fitted and prematurely discharged after being fitted will be described. The reasons for early discharge will also be described.

The analysis populations and number of patients per sub-group will also be described.

X.3.3 - DEMOGRAPHICS AND INCLUSION CHARACTERISTICS

Descriptive statistics (number, mean, standard deviation, median, Q1, Q3, minimum and maximum) will be used to present the inclusion characteristics and demographic data of intent-to-treat patients.

X.3.4 - ANALYSIS OF THE PRIMARY ASSESSMENT CRITERION

To meet the main objective, the overall CSQ-8 score will be calculated at each time of assessment. The percentage of patients satisfied on D30 and D90 and the percentage of patients with continued satisfaction on D90 will be described. The 95% CIs will also be presented.

The absolute variation of the overall CSQ-8 score and the relative variation in relation to D30 will also be described on D90.

Each item of the questionnaire "You and your management by your service provider" will be described at each time of assessment. Scores based on the scales from 1 to 10 will be presented using descriptive statistics.

X.3.5 - ANALYSIS OF SECONDARY ASSESSMENT CRITERIA

Home healthcare provider (PSAD) management

Management description

For each phase of the study (pre-installation, installation and follow-up), the number of interactions will be described. The type of interaction (visits/telephone calls), the time spent per interaction, the main reason and secondary reason for making contact will also be presented.

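### Does the D90 satisfaction percentage need a stated rule for patients without a D90 CSQ-8 score?

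*Combined protocol and SAP*

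**What the plan says.** Section X.3.1 states that "The number of patients is small and the proportion of expected missing or invalid data is small and randomly distributed" and concludes that nothing will be imputed. Any replacement of values is left to the SAP, case by case.

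Section X.3.4 gives the primary analysis: "The percentage of patients satisfied on D30 and D90 and the percentage of patients with continued satisfaction on D90 will be described", with 95% confidence intervals. It names no denominator. The intent-to-treat set in X.2.1 is "all of the included patients fitted with the device who meet all of the inclusion and exclusion criteria", so membership does not depend on having a D90 questionnaire.

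Section X.1 plans 35 patients to obtain 32 evaluable (a term it does not define) and quotes an accuracy of 12.4% or better if at least 85% are satisfied. Patients who leave before fitting are replaced, and section III closes recruitment at 35 fitted.

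The questionnaire schedule in VI.1 uses one column for both D90 and early withdrawal. VI.9 says "An end-of-study visit will be carried out for all patients" and includes the D90 booklet at an early-discharge visit, but only where possible.

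Under X.3 the SAP is still to be drafted, to be "validated by the sponsor before the database is frozen". IX.2 sets the missing-data strategy at a review before lock and requires the decisions to be recorded.

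**The concern.** Three things look loose around the figure that justifies the sample size.

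- **Denominator.** The intent-to-treat definition points to all fitted, eligible patients, while the evaluable count points to those with a score. X.3.4 does not choose.
- **Early-withdrawal scores.** One schedule column governs collection. No section says whether a score given well before the D90 window of ±15 days is analysed as D90. Continued satisfaction is affected too, because it needs both a D30 and a D90 score.
- **Random missingness.** Nothing in the protocol supports it. The reasons for leaving in IV.3 include withdrawal of consent and "Patient lost to follow-up", and either could go with low satisfaction.

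Because pre-fitting losses are replaced and recruitment stops at 35 fitted, the allowance from 35 to 32 falls after fitting, where this gap lies. If the patients without scores were the less satisfied ones, the reported percentage would be too high and its interval would not show it. The rule could also be settled at a review where the data of an open, single-arm study are already tabulated.

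**Working it through.** **Plan's own figure.** X.1 uses E = 1.96 × √(p(1−p)/n). With p = 0.85 and n = 32, E = 1.96 × √(0.1275/32) = 12.4%, which agrees with the protocol. With n = 35 it would be 11.8%. The plan therefore computed the precision of the D90 percentage on the evaluable patients, not on everyone fitted.

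**What no imputation implies.** Reporting 27/35 when three patients have no score classes those three as not satisfied. That is a single imputation, and X.3.1 says none is applied. With the n = 32 above, the plan points to observed cases.

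**Size if the missing differ.** Assumptions: 35 fitted, eligible patients; 32 with a D90 score; 27 of the 32 satisfied (0.85 × 32 = 27.2). Intervals are Agresti-Coull, the method named in X.3.1: with z = 1.96, ñ = n + z², p̃ = (x + z²/2)/ñ, and limits p̃ ± z√(p̃(1−p̃)/ñ).

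Observed cases: 27/32 = 84.4%. Here ñ = 35.84, p̃ = 28.92/35.84 = 0.807 and the half-width is 0.129, giving 67.8 to 93.6%.

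| Satisfied among the 3 missing | Percentage on 35 | 95% CI | Observed minus this |
|---|---|---|---|
| 0 | 27/35 = 77.1% | 60.7 to 88.2 | +7.2 |
| 1 | 28/35 = 80.0% | 63.8 to 90.3 | +4.4 |
| 2 | 29/35 = 82.9% | 66.9 to 92.3 | +1.5 |
| 3 | 30/35 = 85.7% | 70.1 to 94.2 | −1.3 |

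With two missing the range is 27/34 = 79.4% to 29/34 = 85.3%, so the observed figure is at most 5.0 points too high. With one missing it is 27/33 = 81.8% to 28/33 = 84.8%, at most 2.6 points too high.

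Equivalently, the overstatement is (missing/total) × (observed % − % among the missing). If half of the three-patient group were satisfied in expectation, it would be 3/35 × (84.4 − 50) = 2.9 points.

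**Early-withdrawal scores.** If one to three early leavers supply a score beyond the 32, counting it as D90 gives a percentage within the same ranges. This second open point adds no larger error under these assumptions.

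**Collection at withdrawal.** IV.3 stops data collection once a patient has left; VI.9 provides an early-discharge visit. The two fit together if that visit is read as the point of leaving.

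**The case for a change.** The strongest argument for acting is that two competent statisticians could report different primary percentages from the same data, and that the worst case of 7.2 points is more than half of the planned 12.4-point half-width. Deferral is also weak protection: the SAP need only precede the freeze, and the IX.2 review works from tables of the entered data.

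Part of this stands. The denominator is implied rather than written, the randomness claim is unsupported, and the timing allows the rule to be settled with scores visible. That the alternative percentages all lie inside the observed-case interval does not remove bias either, since that interval reflects sampling error only.

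The rest is weaker. The alternative denominator requires an imputation that the plan rules out, so the choice is not evenly balanced. The database goes to the statistician only after the review report is approved and the database locked, and X.4 requires changes of method to be explained in the SAP and the study report. X.3.2 reports numbers and reasons for discharge after fitting, so a reader can approximate the bounds, though not see how early-withdrawal scores were counted. The 7.2 points also needs three patients who are eligible, without a score and all dissatisfied. Some of the three may instead be fitted patients later found ineligible, whom X.2.2 removes from the intent-to-treat set altogether.

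**Conclusion.** This is a gap that analysts fill sensibly, and it calls for no change to the plan. The protocol's own terms lead to an observed-case percentage, which a careful reviewer would also keep as the main figure. Removing the randomness claim would alter no analysis, because the no-imputation choice also rests on the small sample and the small expected proportion missing. A best- and worst-case row would be an optional extra that itself needs an exception to the no-imputation rule.

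Assuming 27 of 32 scored patients are satisfied, the observed percentage could be too high by at most 2.6 points with one eligible patient missing, 5.0 with two and 7.2 with three. It could be too low by at most 0.5, 0.9 and 1.3 points respectively. Dependence of missingness on satisfaction is possible but not shown. The study is descriptive, with no hypothesis test and no success threshold, so the effect is confined to how closely one reads a percentage that is already uncertain by about 12 to 13 points either way.
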